8.8. Vital Signs

Vital signs (blood pressure [systolic/diastolic], pulse and orthostatic changes, respiratory rate, and temperature) will be measured at each in-clinic visit pre-injection. [REDACTED]

[REDACTED] Vital signs will also be measured in the event of an injection site pus-containing lesion (abscess, infection, or inflammation), ulceration, or necrosis (Table 1 and Table 2 of the study protocol).

[REDACTED]
[REDACTED]
[REDACTED]
[REDACTED]
[REDACTED]
[REDACTED]
[REDACTED]
[REDACTED]
[REDACTED]
[REDACTED]

Table 3: Criteria for Potentially Clinically Significant Vital Signs

8.9. Electrocardiography

A standard 12-lead ECG will be recorded at the time points detailed in Tables 1 and 2 of the study protocol. Triplicate measurements (approximately 5 minutes apart) will be performed at screening and baseline and single measurements at other in-clinic visits, as specified at the study protocol.

Electrocardiogram (ECG) findings (normal and abnormal) at screening and baseline will be summarized using descriptive statistics; the data presentation will include both eResearch Technology (the central ECG vendor) and investigator interpretation. The average of the 3 ECG screening and baseline assessments will be calculated; if more measurements are taken, the 3 last measurements taken prior to first dose administration will be used both for the average calculation and for choosing the worst result for the interpretation.

If the investigator interpretation is missing, the following derivation rule will be used:

1. If ERT interpretation is 'normal' then investigator interpretation on the same date will be derived as 'normal';
2. Otherwise investigator interpretation will not be derived.

Shifts (normal and abnormal) from baseline to overall result interpretation at each scheduled visit including "at any visit" assessment (as a separate visit) will be summarized using patient counts.

For overall result interpretation the worst post baseline finding for the patient (the abnormal finding if there are both normal and abnormal findings) will be used in the summaries.

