8.7. Electrocardiography

A 12-lead ECG will be recorded at the time points detailed in [Table 1](#) and [Table 2](#). At screening and baseline, measurements will be done in triplicate (approximately 5 minutes apart). Single measurements will be performed at all other in-clinic visits where ECG recordings are taken. All ECG recordings should be sent to the central diagnostic center at screening, baseline, and throughout the study. A qualified physician at a central diagnostic center will interpret the ECG.

Patients' eligibility at screening may be determined based on the investigator or designee ECG interpretation.

[figure not shown]
In case only local ECGs interpretations are available within the screening period and they indicate that the patient is eligible for randomization, the patient may be randomized (provided all other study eligibility criteria are met). When central diagnostic ECG interpretation becomes available (after randomization), the patient's eligibility should be re-confirmed. In case the central diagnostic interpretation suggest that the patient does not meet study eligibility criteria, it is recommended to repeat the ECG and consult the MM.

All ECG results outside of the reference ranges will be judged by the investigator as belonging to one of the following categories:

- abnormal and not clinically significant
- abnormal and clinically significant

Any ECG finding that is assessed by the investigator as clinically significant (except at the screening visit) will be considered an adverse event, recorded on the source documentation and in the CRF, and monitored as described in Section 8.1.2.

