4.2. Specification of Baseline Values

For Period 1, the baseline value for a patient is the last observed data that was collected for this patient prior to the first IMP dose administration, unless otherwise noted.

For Period 2, the baseline value for a patient is the last observed data that was collected for a patient prior to the third IMP administration (i.e., first administration in period 2, at visit 11, week 8), unless otherwise specified (see procedures and assessments which may be performed after the re-randomization to Period 2 at visit 11 in Section 6.9.1 in the study protocol).

For the integrated periods to be presented in the CSR and during the IDMC closed (in an unblinded manner) and open (in a blinded manner) sessions, the baseline values of patients initially randomized in Period 1 to TV-44749 groups will be defined as the last observed data that was collected prior to the first TV-44749 dose administration. For patients that were assigned to placebo group in Period 1, the baseline value is the baseline value for Period 2 (see above paragraph).

It should be noted that the baseline values of placebo patients will differ between tables presented in the integrated periods summaries and those presented in Period 1 summaries.

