4.4. Study Days and Visits

Study days will be numbered relative to the first day of IMP administration (i.e., the first administration in Period 1). The start of treatment (Day 1) is defined as the date for which a patient receives the first dose of study drug, as recorded on the Case Report Form (CRF). Days will be numbered relative to treatment start (i.e., ..., -2, -1, 1, 2, ...; with Day 1 being the first day of study drug administration and day -1 being the day before the first day of study drug administration).

In case the Early Termination (ET)/End-of-Treatment (EOT) visit occurred on the allowed time window for any scheduled visit (according to Table 1 and Table 2 of the study protocol), and the scheduled visit results are missing, the results from the overlapping ET/EOT visit will be mapped to the scheduled visit.

In case the EOT or Follow-up visit assessments were collected out of the allowed time window, assessment results will be excluded from the by-visit summary tables but will be included in relevant listings. In addition, if there are multiple assessments at a post-baseline visit day, then the last non-missing assessment at that visit will be used, unless otherwise specified.

For the by-visit summary tables, only scheduled visits, EOT and follow-up visits will be presented. The ET visit will not be presented, and unscheduled visits will not be mapped or presented. For the 'at any time' summary statistics in the shift tables and in the presentation of Potentially Clinically Significant (PCS) summaries, all visits will be used (including unscheduled visits).

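### By-visit ECG shift rows compare a worst-of-three baseline with a single later tracing, which understates new abnormality and overstates improvement

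*SAP*

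**What the plan says.** The number of tracings differs by time point. SAP 8.9 states: "Triplicate measurements (approximately 5 minutes apart) will be performed at screening and baseline and single measurements at other in-clinic visits". Protocol 8.7 agrees: "Single measurements will be performed at all other in-clinic visits where ECG recordings are taken".

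SAP 8.9 averages the three pre-dose tracings for numeric values. For the normal/abnormal interpretation it takes the worst: if there are more than three, the last three before the first dose "will be used both for the average calculation and for choosing the worst result for the interpretation".

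The table built on that baseline is: "Shifts (normal and abnormal) from baseline to overall result interpretation at each scheduled visit", with an additional row for any visit. SAP 8.9 continues: "For overall result interpretation the worst post baseline finding for the patient (the abnormal finding if there are both normal and abnormal findings"). For the any-time row of shift tables, SAP 4.4 says that "all visits will be used (including unscheduled visits").

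For the integrated tables SAP 4.2 says: "For patients that were assigned to placebo group in Period 1, the baseline value is the baseline value for Period 2". That is the last observation before the Visit 11 injection, where the schedule provides one tracing. SAP 3.3 counts these patients under the TV-44749 dose they first received in Period 2, in the same dose groups as patients who were on that dose from the start.

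**The concern.** A patient is normal at baseline only if three tracings are all normal, but is normal at Week 4 if one tracing is. Unless readings are perfectly reproducible, the stricter baseline rule moves some patients from normal to abnormal before treatment. Fewer patients are then left to shift from normal to abnormal, and more appear to recover. The by-visit rows would show apparent ECG improvement with no drug effect, and would under-count new abnormalities.

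The worst-finding rule does not restore balance in these rows, because the worst of a single scheduled tracing is that tracing. Nor does SAP 4.4, whose general rule for repeats on one post-baseline visit day is to take the last non-missing value.

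The integrated tables have a second problem that needs no assumed rate. One dose column contains two baseline definitions, and which one applies depends only on the patient's Period 1 arm.

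**Working it through.** The plan states no ECG rate or error figure, so there is nothing of its own to reproduce. The check is what the shift cells would show with no drug effect.

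**Inputs from the documents**
- Baseline tracings: 3 as planned; 1 for former-placebo patients in the integrated tables.
- Tracings in a scheduled-visit row: 1.
- Scheduled post-baseline tracings in Period 1: 2 (Visits 7 and 11, Protocol Appendix B).
- Scheduled tracings over both periods: up to 9 for a completer active from the start (Visits 7, 11, 13, 15, 17, 19, 21, end of treatment, follow-up) and up to 7 for a former-placebo completer.

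**Assumptions (not in the documents)**
- p, the chance that one tracing is read abnormal.
- r, the within-patient correlation of readings.

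**Formulas.** Let F(n) be the chance that n tracings are all normal. For independent tracings F(n) = (1−p)^n. For correlated tracings (beta-binomial), with M = 1/r − 1 and b = (1−p)M, F(n) is the product of (b+i)/(M+i) for i = 0 to n−1. With B baseline and k later tracings:
- normal-to-abnormal (N>A) = F(B) − F(B+k)
- abnormal-to-normal (A>N) = F(k) − F(B+k)

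**Step 1: scheduled-visit rows, p = 20%, r = 0.5.** M = 1 and b = 0.8, so F(1) = 0.800, F(2) = 0.720, F(3) = 0.672, F(4) = 0.6384.
- Planned (3 against 1): N>A = 0.672 − 0.6384 = 3.4%; A>N = 0.800 − 0.6384 = 16.2%. Baseline abnormal is 1 − 0.672 = 32.8%.
- Matched (1 against 1): 0.800 − 0.720 = 8.0% each way.
- Fall in N>A: 1 − 3.36/8.0 = 58%.

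Other assumed values, by-visit rows, shown as N>A / A>N:

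| p | r | 3 against 1 | 1 against 1 |
|---|---|---|---|
| 5% | 0 | 4.3 / 13.5 | 4.7 / 4.7 |
| 5% | 0.6 | 0.8 / 3.9 | 1.9 / 1.9 |
| 10% | 0 | 7.3 / 24.4 | 9.0 / 9.0 |
| 10% | 0.3 | 3.5 / 14.3 | 6.3 / 6.3 |
| 10% | 0.6 | 1.5 / 7.3 | 3.6 / 3.6 |
| 20% | 0.3 | 5.4 / 24.0 | 11.2 / 11.2 |
| 20% | 0.6 | 2.5 / 12.6 | 6.4 / 6.4 |

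The direction is the same in every row.

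**Step 2: allow closer agreement within a session.** Step 1 gives tracings 5 minutes apart the same correlation as tracings weeks apart. Suppose instead that with probability c the three baseline tracings are one reading repeated, and otherwise behave as in step 1. The within-session correlation is then c + (1−c)×0.5.
- c = 0.8 (within-session 0.90): N>A = 0.8×8.0 + 0.2×3.36 = 7.1%, a fall of 12%.
- c = 0.38 (within-session 0.69): N>A = 0.38×8.0 + 0.62×3.36 = 5.1%, a fall of 36%.

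A simulation with p = 20%, within-session correlation 0.9 and between-visit correlation about 0.47 gave 7.6% against 8.4%, a fall of about 10%.

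**Step 3: arm comparison in Period 1.** Let active treatment raise p from 10% to 15%, with independent tracings. The N>A difference is 0.9×5 = 4.5 points with one baseline tracing and 0.729×5 = 3.6 points with worst-of-three, an attenuation of 19%. Among baseline-normal patients it is 5 points under both rules.

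**Step 4: any-visit row, p = 20%, r = 0.5, N>A / A>N.** F(5) = 0.6129.
- Period 1, two later tracings, worst-of-three baseline: 0.672 − 0.6129 = 5.9%; 0.720 − 0.6129 = 10.7%.
- Period 1, single baseline tracing: 0.800 − 0.672 = 12.8%; 0.720 − 0.672 = 4.8%.
- Integrated, 3 against 9: 15.3% / 3.0%.
- Integrated, 1 against 7: 23.9% / 1.4%.

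Here the tilt is smaller in Period 1 and reverses in the integrated tables. A single-tracing baseline would make this row worse in Period 1 (a gap of 8.0 points instead of 4.8, in the opposite direction).

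**Step 5: integrated by-visit rows.** From step 1, with no drug effect, patients active from the start would show 3.4% / 16.2% and former-placebo patients 8.0% / 8.0%, within one dose column.

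**The case against.** A reader might infer that the ECG shift tables hide new abnormalities. The documents do not support that.

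- The any-visit row uses the worst post-baseline finding from all visits, and in the integrated tables it leans towards over-counting new abnormality.
- Period 1 is read by arm against concurrent placebo under one rule, so the comparison is diluted only.
- The normal-to-abnormal shift is not the only ECG safety signal. Protocol 8.7 makes clinically significant findings after screening adverse events, Protocol 10.7 lists values meeting predefined criteria, and SAP 8.1 requires separate on-treatment and follow-up ECG summaries.

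Three further points are fair. Requiring three normal tracings before calling a later abnormality new is a defensible choice for specificity, and with no drug effect the shifts it removes are reading noise. A fall near 60% presumes that tracings 5 minutes apart agree no better than tracings weeks apart, which is unlikely. SAP 4.2 discloses that placebo patients' baselines differ between Period 1 and integrated summaries, and SAP 8.1 separates roll-over patients for closed data monitoring reviews.

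These points limit the size and scope. They do not remove the asymmetry in the scheduled-visit rows, where the specificity gain comes with an excess of apparent recoveries. SAP 4.2 does not say that the number of tracings behind the baseline differs, and SAP 8.1 states no roll-over split for the study report.

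**Conclusion.** The point holds for the scheduled-visit rows and for the integrated dose columns. In the by-visit rows, normal-to-abnormal is understated and abnormal-to-normal overstated in every arm. The fall in normal-to-abnormal is about 10% with close within-session agreement, about a third at a within-session correlation near 0.7, and up to about 60% if sessions give no extra agreement. If that extra agreement is absent, apparent recovery is about two to three times the matched value. All these sizes rest on assumed p and r. The direction rests only on readings being less than perfectly reproducible and otherwise stable.

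The mixed baseline within integrated dose columns follows from the text alone. Numeric ECG parameters, which use the three-tracing average, do not have this bias. The tables are descriptive, so this is a low-cost improvement and not a threat to the trial's conclusions.

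**What to change.** Amend the derivation in SAP 8.9:

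- **Scheduled-visit shift rows, Period 1 and integrated:** take the baseline interpretation from the last single tracing before the first dose (integrated tables: before the first TV-44749 dose). Each row then compares one tracing with one, and both groups in a dose column share a definition.
- **Any-visit row, Period 1:** keep worst-of-three, since the row uses the worst post-baseline finding.
- **Any-visit row, integrated:** add a footnote that it compares unequal numbers of baseline and later tracings.
- **Numeric parameters:** keep the three-tracing average, and list the worst-of-three interpretation separately.

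The cost is a short text change and a changed derivation on data already collected. Two baseline readings go unused in the by-visit rows, and some patients with an abnormal earlier pre-dose tracing may be counted as new abnormalities; the separate listing lets a reader identify them.

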8.10. Concomitant Medications or Therapies

Concomitant therapies and medications, including medications that are taken on an as needed basis and occasional therapies, will be monitored and recorded during the study. Details of prohibited medications may be found in Section 6.7 of the study protocol. All concomitant medications will be coded using the WHO Drug.

The incidence of concomitant therapies and medications will be summarized by therapeutic class category and preferred term using descriptive statistics. Patients are counted only once in each therapeutic class, and only once in each preferred term category. Concomitant therapies and medications will include all medications up to the end of study as defined in the study protocol. This will also include medication that a patient had started taking before entering the study as long as the patient had continued to take this medication during the study.

A separate summary will be presented for Period 1 and for the integrated study periods. A separate safety summaries will be presented for the On Treatment period (baseline visit until EOT visit, including ET if conducted during this period) and for the Follow-Up period (any visit after the End of Treatment/Early Termination visit until the end of the study).

8.11. Post-injection Delirium/Sedation Syndrome

If any PDSS event will occur during the study, the event will be presented as part of the AEs, PDAESI, SAE (if relevant) by Treatment Group. In addition, suspected PDSS cases will be listed.

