3.3. Safety Analysis Set

The safety analysis set for Period 1 will include all randomized patients who received at least 1 dose of TV-44749 or placebo. The safety analysis set for Period 2 will include all randomized patients to Period 2 who received at least 1 dose of TV-44749. For the integrated study periods summary tables (see Section [8](#)) the safety analysis set will include all patients in the safety analysis set of period 1 that received 1 of the 3 TV-44749 treatments groups, or all patients that meet the definition of the safety analysis set of Period 2.

In each of the safety analysis sets, treatment will be assigned based on the initial treatment patients actually received in the corresponding period, regardless of the treatment to which they were randomized, and regardless of dose adjustments, unless otherwise specified. For the integrated periods summary tables, patients randomized in Period 1 to 1 of the 3 TV-44749 groups will be counted according to the initial dose they actually received in Period 1. Patients that were randomized to Placebo in Period 1 will be counted according to the initial dose of TV-44749 they actually received after the re-randomization of those patients to the 1 of the 3 TV-44749 treatment groups in Period 2, regardless of dose adjustment that may occur during Period 2.

In cases of dosing error, a decision of what is the treatment assignment for these patients will be made in a blinded manner prior to unblinding of Period 1, as applicable. The decision will be made during the statistical data review meeting and will be documented in the statistical data review document.

For IDMC monitoring during the study, the safety analysis set will use the treatment based on the randomization assignment in the opening of each period.

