In the case of dose adjustment (which is allowed from Visit 12 during Period 2), the patient will be regarded according to the *initial* dose they actually received in the corresponding period. In addition, separate safety summaries will be generated for AEs, SAEs, exposure to study treatment, potential clinically significant safety measures, excluding the patients with at least one dose adjustment during Period 2. Analysis may also be initiated if the results of those summaries are judged to be significantly different from the results of the safety measurements according to the *initial* actual dose. A separate set of safety tables may be generated in which the patient will be regarded according to the actual dose, by the following exposure duration: ≤ 6 months, > 6 and ≤ 12 months, > 12 months. Each patient may be calculated more than once, according to the exposure duration at each dose.

Analyses will be conducted on the raw values and changes from baseline at each time point, as appropriate. Summaries will be presented by treatment group and overall (total), unless otherwise stated.

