8.2. Duration of Exposure to Study Drug

Duration of exposure to study drug (days) for individual patients will be calculated during the integrated study periods as the number the days patient was exposed to treatment (last day of TV-44749 administration – first day of TV-44749 administration + 28). For patients randomized to placebo in Period 1 who were re-randomized to Period 2, the first TV-44749 injection is at Visit 11 (week 8), the day of re-randomization for Period 2.

Duration of treatment (days) will be summarized for integrated study periods using descriptive statistics. Summaries of the total exposure to TV-44749, will be presented by treatment group, and for overall (total) for patients on active treatment. For an individual patient who was assigned to the placebo group in Period 1, the total duration of exposure will be counted only in Period 2 (the exposure to placebo in the first 8 weeks will not be included in the summary).

Duration of exposure (days) will also be presented by number of injections for the integrated periods using the mutually exclusive categories:

- 0 injections
- 1 injection
- 2 injections
- ≥ 3 to ≤ 6 injections
- ≥ 7 to ≤ 9 injections
- ≥ 10 to ≤ 12 injections
- > 12 injections

In addition, summary of exposure to study TV-44749 doses will be calculated using the categories:

- < 6 months
- ≥ 6 to < 12 months,
- ≥ 12 months.

The total number of TV-44749 injections by dose and overall (total) will be presented. Exposure categories including at least 6 and 12 months are defined as at least 6 and 12 injections plus 28 days following the last injection, respectively.

All summary tables for duration of exposure will be presented by treatment group and overall (total).

Unless otherwise specified, in cases where there was a dose adjustment, exposure will be calculated according to the *initial* actual dose received in Period 1 (or the initial actual dose received in Period 2) regardless of dose adjustments. In addition, separate safety summaries will be generated, excluding the patients with at least one dose adjustment event during the study.

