If the results of those summaries are judged to be significantly different from the results of duration of exposure summaries according to the randomized dose, additional analyses will be conducted. These analyses may include shift tables of randomized dose to dose adjustments. If the proportion of patients with dose adjustment will be high, additional table according to the actual cumulative exposure by dose will be presented. For this table a patient may contribute to more than 1 dose level, and the duration of exposure at each dose will be determined by the time from 1st administration of the dose to the day of the dose adjustment minus 1 or the last administration, as appropriate. For example if a patient that was re-randomized to medium dose following placebo in Period 1, and then underwent a dose adjustment to the high dose for the 3rd injection, this dose will be used until the end of study. Thus, assuming that all injections are administered exactly 28 days apart, the patient will contribute $2*28-1= 55$ days to the medium dose group, and $28*10=280$ days to the high dose group.

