8.4. Adverse Events

Adverse events will be collected and recorded from the time a patient signs the informed consent to the end of follow-up period.

All adverse events will be coded using the Medical Dictionary for Regulatory Activities (MedDRA version 26.0 or later). Unless otherwise specified, adverse events will be summarized by SOC and preferred term, with preferred terms within SOCs presented in descending order of patient incidence. Multiple records with the same PT or SOC category and adverse event onset date for the same patient, or with overlapping or consecutive dates, are counted only once for the adverse event with the highest severity and seriousness.

Adverse events summaries will be presented for Period 1 separately and for the integrated study periods separately. Adverse events that started in Period 1 and ended in Period 2 will be reported only in Period 1, and will be presented only once in the integrated summary table.

Summaries will include treatment-emergent adverse events that are defined as adverse events that occurred at or after the first IMP injection was administered through the end of the treatment (including the assessment collected in the End-of-Treatment/ Early Termination visit).

Additional summaries will be presented for the follow-up period (after the End of Treatment/Early Termination visit and until the end of the study).

Summaries will be presented for all adverse events (overall and by severity), including adverse events defined by the investigator as related or with missing relationship to IMP treatment and/or device (overall and by severity), serious adverse events, serious adverse device events and adverse events and adverse device events causing withdrawal from the study and withdrawal from the treatment. All summaries will be presented by treatment group and overall (total), using exposure categories.

Protocol defined adverse event of special interest (PDAESI) (section 8.1.7 of the study protocol) will also be summarized and presented by treatment group and by visit..

The summary tables for adverse events will be presented by the treatment group to which the patient were assigned according to the safety analysis set. A separate summary tables will be presented, excluding the patients with at least one dose adjustment. Additional analysis may be initiated if the results of those summaries will judged by the study team to be significantly different.

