Patient listings of serious adverse events, adverse events leading to treatment discontinuation and study withdrawal, and adverse events leading to death will be presented. Patient's dose at the time of the Adverse Event onset will be included in all listings.

In case of the missing dates and severity, the imputation will be performed as described in Section 4.3.

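### After a dose change, PDSS is tabulated under the initial dose rather than the dose injected, and no required table in the readable SAP joins PDSS to injections or gives an interval

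*SAP*

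**What the plan says.** SAP 8.11 is short: "If any PDSS event will occur during the study, the event will be presented as part of the AEs, PDAESI, SAE" (the last where relevant), by treatment group, with suspected cases also listed. The meaning of treatment group comes from other sections.

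- SAP 3.3: "treatment will be assigned based on the initial treatment patients actually received in the corresponding period", with later adjustments ignored unless specified otherwise.
- SAP 8.1: "In the case of dose adjustment (which is allowed from Visit 12 during Period 2), the patient will be regarded according to the" initial dose actually received. Safety tables by actual dose are optional.
- SAP 8.4 uses the safety-set group for the adverse event tables and adds: "A separate summary tables will be presented, excluding the patients with at least one dose adjustment".
- SAP 8.2: unless specified otherwise, "in cases where there was a dose adjustment, exposure will be calculated according to the" initial actual dose. It also says: "If the proportion of patients with dose adjustment will be high, additional table according to the actual cumulative exposure by dose will be presented". No threshold for high is given.

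Three planned outputs limit the problem.

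- SAP 8.4: "Patient's dose at the time of the Adverse Event onset will be included in all listings".
- SAP 8.4 also presents protocol-defined adverse events of special interest (PDAESI), where SAP 8.11 places PDSS, by visit as well as by group.
- SAP 8.2 plans a count of TV-44749 injections, by dose and in total.

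**The concern.** PDSS belongs to a single injection. For the intramuscular product, Protocol 2.2.2.2 gives a median onset of 25 minutes and links events to raised plasma concentrations in the first hours after the injection concerned. The dose that matters is the one given that day, not the one the patient started on. The two can differ: investigators may change the dose from Visit 12, and Protocol 6.9.4 foresees further changes once topline results are known.

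PDSS is also a result readers will look for. Protocol 2.1.2.2 says the precautions needed for the intramuscular product, which centre on PDSS, are why it is rarely used. With few or no events, the informative result is the per-injection risk that the trial can exclude, overall and at each dose injected. A count or a 0% under the initial dose does not give that.

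**Working it through.** **1. The attribution rule, on the SAP's own example.** SAP 8.2 describes a former placebo patient assigned the medium dose in Period 2, who then "underwent a dose adjustment to the high dose for the 3rd injection, this dose will be used until the end of study". Its exposure figures reproduce: 2 × 28 − 1 = 55 days medium and 28 × 10 = 280 days high. In injections, that is 2 medium and 10 high, so 10/12 = 83% are at the high dose. A PDSS event after any of those 10 would be handled as follows:

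- main table: counted under medium (SAP 3.3, 8.1, 8.4, 8.11);
- companion table: absent, because the patient is excluded (SAP 8.4);
- actual-dose safety tables: produced only if the team chooses (SAP 8.1);
- listing: shown with the high dose (SAP 8.4).

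Protocol 10.7 would allow the adjusted dose to apply from its first administration. The SAP prevails, and SAP 17 does not list this change.

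**2. Which injections can be affected.** The dose is fixed at weeks 0, 4 and 8. Only the injections at Visits 12 to 22 can differ from the initial dose: at most 11 of 14 TV-44749 injections in a patient randomized to active treatment, and 11 of 12 in a former placebo patient. The documents do not say how many patients will change dose.

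Assume, for illustration, 2,000 injections per initial-dose group, with a fraction f of the low- and medium-group injections given at the high dose. The share of all high-dose injections filed under another dose is 4,000f / (2,000 + 4,000f). For f = 5%, 10%, 20% and 30% this is 9%, 17%, 29% and 38%.

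**3. What zero events would exclude.** The documents state no PDSS rate, target or interval, so there is no figure to reproduce. Inputs:

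- about 640 randomized 1:1:1:1, with about 440 completing week 8 (Protocol 10.1), so 440/640 = 68.75%;
- active arms: 480 patients, of whom 330 complete; placebo: 160 patients, of whom 110 complete;
- 2 injections in Period 1 and up to 12 in Period 2 (Protocol 1.1).

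Assumptions: the completer fraction is equal across arms, all completers enter Period 2, active non-completers receive one injection, and completers receive a mean of m injections in Period 2.

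Total TV-44749 injections n = 330 × (2 + m) + 150 × 1 + 110 × m. With zero events, the exact two-sided 95% upper limit is 1 − 0.025^(1/n).

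| Scenario | n | Upper limit, overall | Upper limit, one dose with n/3 |
|---|---|---|---|
| m = 12 | 6,090 | 0.061% | 0.18% |
| m = 6 | 3,450 | 0.107% | 0.32% |
| m = 3 | 2,130 | 0.173% | 0.52% |
| No dropout: 480 × 14 + 160 × 12 | 8,640 | 0.043% | 0.13% |

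If active non-completers receive two injections, each of the first three totals rises by 150. With 675 randomized (the number in the amendment rationale) and the same completer fraction, the first three totals become 6,423, 3,639 and 2,246, with limits of 0.057%, 0.101% and 0.164%. One event in 3,450 injections gives an interval of 0.0007% to 0.161%. Per patient, 480 + 110 = 590 exposed with zero events gives an upper limit of 0.623%.

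**The case against.** The strongest reply is that this is a presentation preference in a descriptive safety section. The overall event count and the overall injection total are both planned outputs, and dose attribution affects neither, so anyone can compute the overall bound. Suspected cases are listed, the listings give the dose at onset, the PDAESI table shows the visit, and the IDMC adjudicates each suspected case (SAP 2.3, 2.6.1). With a handful of events, a reader would go to the case listing. Nor do the readable documents argue that PDSS depends on dose: Protocol 2.3.1 describes a proposed mechanism for the intramuscular product of vessel injury and rapid dissolution of the pamoate salt.

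Most of this stands, and it rules out several stronger inferences.

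- A reader might infer that an event could be hidden. It could not, because the listings retain it with its dose.
- A reader might infer that no injection denominator is planned. SAP 8.2 plans one.
- A reader might take 83% as the extent of misattribution. It describes one hypothetical patient.
- A reader might infer that no PDSS rate is planned anywhere. Protocol 8.10, the PDAESI definitions, the exploratory endpoints and the PDSS procedures in SAP 2.1 are blacked out, and the IDMC charter is not available. The absence can be stated only for the readable text.

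The reply does not repair the by-dose count. The by-visit table still uses the initial-dose group. The companion tables delete the event instead of moving it. Further adverse event analysis depends on the team judging results significantly different, which one or two rare events are unlikely to trigger. The injection count by dose is also ambiguous, because SAP 8.2 defaults to initial dose for exposure.

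**Conclusion.** The point holds in limited form. The SAP's stated rule gives a wrong by-dose count for an acute, injection-linked event, but only from Visit 12 onward and only while the current dose differs from the initial one. The total amount misfiled cannot be estimated from the documents. Overall PDSS risk is unaffected by attribution and can be derived from planned outputs. What the readable plan lacks is a required table that joins events to injections by dose actually given, with an interval.

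The injection totals and limits above are illustrations under assumed exposure. They are not errors in the plan, and no planned conclusion is shown to change. They do show why a bare zero is uninformative: across these scenarios the overall limit varies about fourfold (0.173/0.043). This is a cheap improvement to reporting.

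**What to change.** In SAP 8.11, pre-specify one table:

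- PDSS confirmed by the IDMC as meeting all five criteria, and separately all suspected PDSS;
- numerator by the dose given at the index injection;
- denominator from the SAP 8.2 injection count, stated to be injections by dose actually given, for each dose and overall;
- exact two-sided 95% Clopper-Pearson intervals, reported even with zero events;
- per-patient incidence alongside, because injections cluster within patients and the per-injection interval treats them as independent (Protocol 2.2.2.2 reports 30 cases in 29 patients for the intramuscular product).

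The cost is one or two sentences and one small table. No new data are needed: injections are recorded and dose adjustments are documented in the CRF. The existing initial-dose tables can stay as they are.
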